16.7 Sponsor's Responsibilities

- Anika Therapeutics, Inc. may delegate some of the responsibilities to a CRO but will maintain oversight of the clinical study. Anika shall define, establish and allocate all the roles and responsibilities related to the clinical study in one or more written agreements.
- Anika Therapeutics, Inc. shall implement and maintain written clinical quality procedures to ensure that the clinical study is designed, conducted and monitored, and that data are generated, documented, recorded and reported in compliance with ISO 14155:2011 and ICH E6, this protocol, any subsequent amendments, and any other applicable standards and regulatory requirements.
- Anika Therapeutics, Inc. will ensure that there is written agreement with the Investigator/institution and any other parties involved with the clinical study.
- Anika Therapeutics, Inc. will designate appropriately qualified medical personnel to advise on medical questions or problems.
- Anika Therapeutics Inc. will utilize appropriately qualified individuals to supervise the overall conduct of the trial, to handle the data, to verify the data, to conduct the statistical analyses, and to prepare the trial reports.
- Anika Therapeutics, Inc. will select Investigators/institutions that are qualified by training and experience with adequate resources to properly conduct this trial for which the Investigator is selected. Anika will also select a coordinating Investigator, if appropriate. Anika Therapeutics,

Inc. will ensure members of the site staff and their designated authorization(s) are identified in a log with details.

- Anika Therapeutics, Inc. will ensure that all Investigators and all other parties involved are given instructions on uniformly assessing and documenting clinical and laboratory findings.
- Anika Therapeutics, Inc. will designate or appoint one or more monitors, or otherwise assume the responsibilities of the monitor(s) and ensure documentation of training, experience and scientific or clinical knowledge for all the relevant parties involved in order to adequately conduct the clinical study. This includes training on the following:
 - Accountability procedures
 - Investigator's Brochure
 - Protocol
 - eCRFs and instructions for completion
 - The written ICF and informed consent process as well as other written information provided to subjects
 - Sponsors written procedures; ISO 14155:2011; and any other applicable regulatory procedures.
- Anika Therapeutics, Inc. will receive disclosures of conflicts of interest from PIs and Investigators.
- Anika Therapeutics, Inc. will assure the accuracy of any translations, as applicable.
- Anika Therapeutics, Inc. will establish an IDMC to assess the progress of a clinical study, including the safety data and the critical efficacy endpoints at intervals, and to recommend to the Sponsor whether to continue, modify, or stop a trial.
- Anika Therapeutics, Inc. will ensure that any electronic trial data handling and/or remote electronic trial data systems, are validated with the following characteristics:
 - Data changes are allowed with an audit trail;
 - System is secure and does not allow for unauthorized access to the data;
 - A list of the individuals who are authorized to make data changes is maintained;
 - Adequate backup of the data is maintained;

- An unambiguous subject ID is used to allow identification of all the data reported for each subject.
- Anika Therapeutics, Inc. will ensure maintenance of sponsor-specific essential documents pertaining to the trial in conformance with the applicable regulatory requirement(s) of the country(ies) where the product is approved, and/or where the sponsor intends to apply for approval(s).
- Anika Therapeutics, Inc. will inform the Investigator/institution in writing of the need for record retention and will notify the Investigator/institution in writing when the trial related records are no longer needed.
- Anika Therapeutics, Inc. will provide insurance or indemnify the Investigator/institution against claims arising from the trial, except for claims that arise from malpractice and/or negligence.
- Anika Therapeutics, Inc. will obtain the following information documentation from each participating EC:
 - The name and address of the EC.
 - A statement obtained from the EC that it is organized and operates according to GCP and the applicable laws and regulations.
 - Documented EC approval/favorable opinion for the protocol and any subsequent amendments (as applicable) and re-approvals.
- Anika Therapeutics, Inc. will update the Investigator's Brochure as significant new information becomes available.
- Anika Therapeutics, Inc. will ensure the CTM is transported at the acceptable storage temperatures and transport conditions.
- Anika Therapeutics, Inc. will verify that each subject has consented, in writing, to direct access to his/her original medical records for trial-related monitoring, audit, EC review, and regulatory inspection.
- Anika Therapeutics, Inc. is responsible for the ongoing safety evaluation of the CTM.
- Anika Therapeutics, Inc. will notify all concerned Investigators/institutions and the regulatory authority(ies) of findings that could affect adversely the safety of subjects, impact the conduct of the trial, or alter the EC approval/favorable opinion to continue the trial.

- Anika Therapeutics, Inc. will submit any required application(s) to the appropriate authority(ies) for review, acceptance, and/or permission (as required by the applicable regulatory requirement(s)) to begin the trial(s).
- Anika Therapeutics, Inc. will ensure that all required EC, or other regulatory approvals are obtained and documented; and that appropriate provisions are made to meet any specific conditions imposed by the EC. Anika will ensure that any modification(s) required by the EC or other regulatory authority are made and documented by the PI and have gained the approval of the EC or other regulatory authority.
- Anika Therapeutics, Inc. will expedite the reporting to all concerned Investigator(s)/institutions(s), to the EC, where required, and to the regulatory authority(ies) of all ADEs that are both serious and unexpected.
- Anika Therapeutics, Inc. will submit to the regulatory authority(ies) all safety updates and periodic reports, as required by applicable regulatory requirement(s).
- Anika Therapeutics, Inc. will ensure that an ongoing risk analysis, based on existing knowledge of the type of product and its intended use, is performed and provided to the Investigator involved in a clinical study with the CTM, through the Investigator's Brochure or updates to it and to the subject through the ICF or updates to it.
- Anika Therapeutics, Inc. will also incorporate the risk analysis and risk management plan of the CTM and share this with the Investigators;
- Anika Therapeutics, Inc. shall be responsible for:
 - Documenting correspondence with all parties involved in the clinical study, including the EC and regulatory authorities;
 - Ensuring that the clinical study is appropriately monitored by determining the extent and nature of the monitoring;
 - Reviewing the monitoring reports and follow-up on actions required in the monitoring report;
 - Taking prompt action to secure compliance with all clinical study requirements;
 - Submitting progress reports, including safety summary deviations, when requested, to all reviewing EC's and the regulatory authorities.

16.8 Informed Consent

All subjects in this study are to be completely informed, in accordance with local EC or other regulatory authority requirements, concerning the pertinent details and purpose of the study. Informed consent for each subject will be obtained in accordance with ICH Guidance for Industry E6 Good Clinical Practice: Consolidated Guidance (ICH Topic E 6 (R1) Guideline for Good Clinical Practice). One copy of the signed ICF document must be given to each subject in his/her native language and one signed copy must be retained in the subject's file.

All subjects must sign and personally date an approved ICF after receiving detailed written and verbal information about the reason, the nature and the possible risks associated with the administration of the CTM. An ICF will be required for all subjects.

All foreseeable risks and potential benefits which might occur with the use of the CTM will have been discussed with the subject. The subject will be informed that, should an unanticipated adverse product-related event occur, which presents an unreasonable risk to participating subjects, he/she will be notified. The subject will be informed that his/her medical records are subject to review by representatives of the Sponsor, EC, or the appropriate regulatory authorities, as necessary. The subject will be informed that the information obtained during the study will be used to evaluate the safety and efficacy of the CTM. However, his/her confidentiality will be maintained at all times. The subject will be told that he/she is free to refuse study participation or to withdraw from the study at any time without compromising future medical care.

The subject must be made aware and agree that personal information may be scrutinized during an audit by competent authorities and properly authorized persons. However, personal information will be treated as strictly confidential and will not be publicly available.

A sample ICF template with standard wording suggested for this study will be provided to each Investigator. Prior to EC submission, the Investigator must send a copy of the ICF to be used at their institution to Anika Therapeutics Inc. or designee for review to assure compliance with the ICH requirements. The approved written consent form is to be supplied by the Investigator and will be understood and signed by each subject prior to enrolling in the study. An ICF will be required for all subjects. The Investigator is responsible for maintaining each subject's ICF in the study file and providing each subject with a copy of the ICF.

16.9 Protocol Adherence

The Investigator agrees to conduct the study according to the protocol and agrees that all persons delegated to perform study procedures will do so as well. The Investigator must read the protocol

thoroughly and must follow the instructions exactly. Investigators shall propose to Anika Therapeutics, Inc. any appropriate modifications to the Protocol. Any change should be agreed to by prior discussion between Anika Therapeutics Inc. and the Investigator, with written protocol amendments made prior to affecting the changes agreed upon. The Investigator is not to conduct any protocol modifications without prior written permission from Anika Therapeutics Inc. Investigator will refrain from implementing any modifications to the protocol without agreement from the Sponsor, EC and regulatory authorities, if applicable. Each Investigator will be responsible for enrolling only those subjects who have met protocol eligibility criteria.

Deviations from the protocol include, but are not limited to, the use of prohibited medications or therapies, out of window visits, etc. All protocol deviations should be documented and explained. Major protocol violations are defined as those that could impact the efficacy evaluation such as a subject is ineligible, missing key data, received an unauthorized treatment, etc. All subjects with protocol deviations will continue to be followed for safety and efficacy assessments. Analysis of study data will be done on both the ITT and PP populations.

16.10 Adverse Event Reporting

The Investigator agrees to document and report all AEs / ARs to Anika Therapeutics, Inc. or its designee. The Investigator is further responsible for ensuring that any Sub-Investigator promptly brings AEs / ARs to the attention of the Investigator. The Investigator is also responsible for informing the participating EC and other regulatory authorities (as applicable) of any reportable events and adhering to local EC requirements. The Investigator agrees to supply Anika Therapeutics Inc., upon request, any additional information related to the safety reporting of a particular event. The Investigator shall inform the subject of the nature and possible cause of any AEs/ ARs experienced.

16.11 Permission to Review Subject's Source Records

The Investigator agrees that Anika Therapeutics, Inc., its employees or agents, and the respective Competent Authorities will have the right from time to time, both during and after this trial, to audit and review pertinent medical records related to the clinical study. A signed statement will be obtained from each subject who participates in the trial that permits the release of his or her medical records as necessary for inspection by authorized personnel from Anika Therapeutics, Inc., its designee or participating Competent Authority. Subjects will not be identified by name, and confidentiality of information in medical records will be preserved.

16.12 Change in Investigator

If any Investigator retires, relocates, or withdraws from an investigation, the responsibility for conducting the study and maintaining records may be transferred to another person who will accept the responsibility at the same institution. Anika Therapeutics, Inc. must be notified of and agree to the change.

16.13 Records Retention

All documents related to this clinical study should be kept in appropriate study files. Copies of the protocol, subject ID, eCRF, source data, ICF and other documents pertaining to the study conduction must be retained until at least 5 years after study completion or longer depending on the applicable regulatory requirements. It is the responsibility of the Sponsor to inform the Investigator/institution as to when these documents no longer need to be retained. No study document will be destroyed without prior written agreement between Anika Therapeutics, Inc. and the Investigator.

16.14 Study Monitoring

An appropriate representative of Anika Therapeutics, Inc. or designee (Study Monitor) will maintain contact with the Investigator and will contact the Clinical Trial Site for the purpose of overseeing the progress of the study, and ensuring it is conducted, recorded and reported in accordance with the protocol, SOPs, GCP and applicable regulatory requirements.

An initiation visit will have been made by the Study Monitor to discuss the Cingal 16-02 protocol and the obligations of both the Sponsor and the Investigator. The Investigator must allow the Study Monitor to perform periodic, interim monitoring visits. The purposes of these visits are:

- Verify that written informed consent was obtained prior to each subject's participation in the trial
- Ensure the conduct of the trial is in compliance with the currently approved protocol/amendment(s), with GCP, and with the applicable regulatory requirement(s)
- Ensure the rights and well-being of human subjects are protected
- Ensure the reported trial data are accurate, complete, and verifiable from source documents.
- Assess the progress of the study
- Review the compliance with the study protocol

- Determine whether the Investigator is maintaining the essential documents
- Discuss any emergent problem(s)
- Act as the main line of communication between the Sponsor and the Investigator
- Ensure that the Investigator receives the current Investigator's Brochure, all documents, and all trial supplies needed to conduct the trial properly and to comply with the applicable regulatory requirement(s)
- Ensure that the Investigator and the Investigator's site staff are adequately informed about the trial
- Verify that the Investigator and the Investigator's site staff are performing the specified trial functions, in accordance with the protocol and any other written agreement between the Sponsor and the Investigator/institution, and have not delegated these functions to unauthorized individuals
- Verify that the Investigator is enrolling only eligible subjects
- Inform the Investigator of any eCRF entry error, omission, or illegibility
- Determine whether all AEs are appropriately reported within the time periods required by GCP, the protocol, the EC, the Sponsor, and the applicable regulatory requirement(s)
- Communicating deviations from the protocol, SOPs, GCP, and the applicable regulatory requirements to the Investigator and ensuring that the site staff takes appropriate action designed to prevent recurrence of the detected deviations

All data required by the protocol must be reported accurately on the eCRFs and must be consistent with the source documents. Source documents are original documents, data and records (e.g., hospital records, clinical and office charts, laboratory notes, memoranda, subjects' diaries or evaluation checklists, pharmacy dispensing records, recorded data from automated instruments, copies or transcriptions certified after verification as being accurate and complete, microfiches, photographic negatives, microfilm or magnetic media, X-rays or other diagnostic images, subject's files, pharmacy records and laboratory records). The Investigator will make available the source documents for inspection. This information will be considered as confidential.

The Study Monitor will perform a closeout visit at the conclusion of the Investigator's involvement in the study.

16.15 Case Report Form

Electronic Case Report Forms must be completed for each subject in accordance with the DMP and any eCRF Completion Guidelines. The Investigator must ensure data are reported into the eCRF in a timely fashion and that data recorded in the eCRF is consistent with the source documents or the discrepancies should be explained. Any change or correction should have an audit trail and explanation of the change.

16.16 Auditing

The Investigator will make all pertinent records available including source documentation for inspection by regulatory authorities and for auditing by the Sponsor. This information will be considered as confidential. The Sponsor's audit will be independent of and separate from routine monitoring or quality control function and will serve to evaluate the trial conduct and compliance with the protocol, SOPs, GCP, and the applicable regulatory requirements.

16.17 Use and Publication of Study Results

All unpublished documentation (including the protocol, eCRF and Investigator's Brochure) given to the Investigator is strictly confidential. All recipients must agree not to disclose the information herein contained to any person without the prior written authorization of Anika Therapeutics, Inc. The submission of these documents to the EC is expressly permitted. The Investigator agrees that Anika Therapeutics, Inc. maintains the right to use the results of this study in their original form and/or in a global report for submission to governmental and regulatory authorities of any country.

The results of the study may be presented during scientific symposia or published in a scientific journal only after review by Anika Therapeutics, Inc. in accordance with the guidelines set forth in the applicable publication or the Investigator agreement.

16.18 Confidentiality

All information that is provided to the Investigator dealing with the CTM is regarded as confidential. Subjects will be told that data will be handled in compliance with Health Insurance Portability and Accountability Act (HIPAA), European Union Data Protection Directive and other national laws on the protection of personal data. Subjects will be informed that the Anika Therapeutics, Inc. or designee will have access to their medical records. Subject's participation in the study will be treated as confidential and subject's will not be referred to by name in any report of the study. The identity of the subjects will not be disclosed in any study records and subjects' data will be described with a unique subject

identifier. Subject data will be processed electronically to determine the outcome of this study, and to provide to health authorities. Subjects will be advised that all data may be transferred to other countries.

16.19 Early Study Discontinuation

If the Sponsor, Investigator, or Study Medical Monitor discover conditions during the study that indicate that the study or Clinical Trial Site should be terminated, this action may be taken after appropriate consultation between the Sponsor, Investigator, and Study Medical Monitor.

Conditions that may warrant termination of the Clinical Trial Site include, but are not limited to:

- The discovery of any unexpected, serious, or unacceptable risk to subjects enrolled in the study,
- The decision on the part of the Sponsor to suspend or discontinue testing, evaluation, or development of the CTM.
- Failure of the Investigator to comply with GCP guidelines,
- Submission of knowingly false information from the research facility to the Sponsor, Clinical Monitor, or regulatory authorities,
- Insufficient adherence to protocol requirements.

If Anika Therapeutics, Inc. and/or the Investigator should discover conditions arising during the study that indicate it should be terminated, an appropriate schedule for termination will be instituted. Anika Therapeutics, Inc. also reserves the right to discontinue this study for administrative reasons at any time.

If a trial is suspended, Anika Therapeutics Inc. will promptly inform the Investigators/institutions, and the regulatory authority(ies) of the termination or suspension and the reason(s) for the termination or suspension. The Investigator should notify the EC promptly and provided the reason(s) for the termination or suspension by the Sponsor or by the Investigator/institution.

16.20 Subject Withdrawal

Each subject is free to discontinue from the study at any time, for any reason. If a subject discontinues the study, the Investigator will record the reason for withdrawal on the eCRF. Examples of reasons for premature withdrawal of a subject from the study include:

- Inter-current illness that would, in the judgment of the Investigator, affect study assessment to a significant degree
- Subject noncompliance with follow-up assessments

- Subject request to withdraw
- Subject lost to follow-up
- Termination of the site's study participation by Anika Therapeutics, Inc., the institution, EC or other regulatory authority
- Other (reason to be documented in the eCRF)

Every effort shall be made to have withdrawn subjects return for the required safety evaluations as detailed in the protocol.

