2 DEFINITIONS

Baseline: The assessments performed prior to the study injection after the Screening Visit.

Blinded Evaluator: The Blinded Evaluator will be a physician, research nurse, registered physiotherapist or physician assistant trained by the PI to perform the assessments outlined in the protocol. The Blinded Evaluator will complete the physical evaluation of both knees, range of motion (ROM) assessment of both knees, and the Evaluator Global Assessment.

End of Study: End of study is defined as the last subject's last visit.

Enrolled: A subject who has signed the informed consent form (ICF) is enrolled.

Index Knee: The knee that meets the eligibility criteria for treatment. The index knee may also be termed the "study knee". In subjects with bilateral knee Osteoarthritis (OA), where both knees meet eligibility criteria, the more symptomatic knee is the index knee.

Ethics Committee (EC): EC refers to an independent body (e.g. Research Ethics Boards, Independent Ethics Committees) whose responsibility is to ensure the protection of rights, safety and well-being of human subjects involved in a trial. Committees with these responsibilities will be referred to in this document as Ethics Committees.

Rescue Medication: Acetaminophen/paracetamol will be distributed as the rescue medication. It is the only medication that should be taken for knee pain during the entire study. Rescue medication will be discontinued at least 48 hours prior to Baseline and all follow-up visits.

Treating Physician: The Treating Physician will most often be the Principal Investigator (PI). He/she will administer the Cingal®, Monovisc® or steroid injection but will not participate in the efficacy evaluation.

Treatment Failure: A subject who undergoes a procedure or uses a medication (other than the rescue medication) for the treatment of OA in the index knee at any time after the study injection through the 39 week visit.

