Subjects meeting the inclusion/exclusion criteria for Cingal 16-02 will have been randomized to receive a single injection of Cingal, Monovisc or triamcinolone hexacetonide (TH) in the index knee. Since there is a difference in volume between Cingal, Monovisc and TH, the treating physician is not considered blinded. To maintain the double-blind design of the study, there is a person assigned to the role of Treating Physician and one person assigned to the role of Blinded Evaluator. The Treating Physician, most often the PI, will administer the injection but will not participate in the evaluation of study treatment effectiveness. A second individual, designated as the Blinded Evaluator, is blinded to treatment and will complete the pre- and post-treatment Evaluator Global Assessment, knee exams and ROM measurements. To maintain the subject blinding, the injection syringe will have been prepared separate from the patient and the injection will be masked from the subject. The blinding of the patient and the blinded evaluator will be maintained in both the Cingal 16-02 and Cingal 17-02 trials.

The subject will have been trained on how to complete the WOMAC, Patient Global Assessment and

EuroQol within the Cingal 16-02 trial. The subject should complete these questionnaires prior to any physical evaluation that must be done at the 39 week follow-up visit.

The Blinded Evaluator will collect and record AEs from the subjects and consult the Treating Physician only as needed in the management of AEs. The Blinded Evaluator will be a physician, research nurse, registered physiotherapist or physician assistant trained to perform the assessments outlined in the protocol (Section, 10.1 Schedule of Events).

Up to 40 sites in Europe are participating in the study to enroll 576 subjects. Subject participation in this extension study will last approximately 13 additional weeks beyond the Cingal 16-02 trial with follow-up the visit scheduled at weeks 39 after the treatment injection in Cingal 16-02.

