10.4 Post-Treatment Follow-Up

All study subjects will have follow-up assessments at 39 weeks after injection day in Cingal 16-02 to evaluate effectiveness of the treatment and to assess AEs and protocol compliance. The Blinded Evaluator will evaluate the clinical status of the subject at each visit.

More than 48 hours prior to the visit, the subject will be reminded of the visit date and time, the need to abstain from acetaminophen/paracetamol for at least 48 hours prior to each follow-up visit and the requirement to bring their subject diary and the acetaminophen/paracetamol for a pill count with them to the appointment.

If the subject arrives for a study visit without discontinuing acetaminophen/paracetamol for at least 48 hours prior to the visit, the visit should be rescheduled within the allowed window of time. Study assessments should be performed as soon as possible and the protocol deviation, if applicable, recorded in the source and eCRF. The subject must be re-educated about the importance of protocol compliance.

If the subject does not come in at the expected time, at least three attempts will be made to contact the subject in order to accomplish maximum subject compliance with the follow-up schedule.

The following post-treatment visits will be performed. The subject will be asked whether any concomitant medications have been taken. All assessments will be done by the Blinded Evaluator.

39 Weeks \pm 7 Days

- Confirm Rescue Medication Washout
- Evaluate Subject Diary
- Count Rescue Medication Pills (if needed)
- Physical Evaluation (both knees)
- ROM (both knees)
- WOMAC (both knees)
- Patient Global Assessment
- Evaluator Global Assessment
- EuroQol
- Assess Concomitant Medications

- Assess AEs

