11.5 Reporting

11.5.1 Adverse Events

All AEs that occur after signing the ICF will be recorded. At each visit during the trial, AEs that have occurred since the previous visit must be recorded. All subjects will be questioned and evaluated for

AEs or complications associated with the procedure. Complications of the injection include, but are not necessarily limited to: pain, swelling and/or inflammation at the injection site. The Investigator will determine the severity and relationship of each event, as defined above.

AEs observed during the course of this study, regardless of severity or relationship to the injection will be recorded on the appropriate eCRF. Each reported complication/AE will also include the duration, action taken to address the AE, and the resolution status (e.g. ongoing, resolved). These subjects will continue to be evaluated for safety and efficacy at all scheduled follow-up points.

The sponsor must report the results of an evaluation of an unanticipated adverse device effect (UADE) to relevant regulatory agencies and all reviewing ECs and investigators within timelines required by the regulatory agencies.

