12.1.1 Primary Efficacy Endpoint

The primary efficacy endpoint is the responder rate as identified by the OMERACT-OARSI responder index at 39 weeks post treatment comparing the Cingal group to the triamcinolone hexacetonide group

The response rate for the Cingal group and Triamcinolone Hexacetonide (TH) group will be calculated and tested using Fisher's exact test. Formally, the hypothesis to be tested is:

$$H_0: \pi_C = \pi_T \text{ versus } H_A: \pi_C \neq \pi_T$$

Where π_C is the responder rate for the Cingal group and π_T is the responder rate for the triamcinolone hexacetonide group.

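### Withdrawn subjects are asked back for safety evaluations but not for week-39 efficacy assessments, so a health-linked withdrawal can lose primary data that could have been collected

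*Protocol*

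**What the plan says.** Protocol 16.20 gives examples of reasons for premature withdrawal. One is "Inter-current illness that would, in the judgment of the Investigator, affect study assessment to a significant degree". The section closes with the follow-up owed to anyone withdrawn: "Every effort shall be made to have withdrawn subjects return for the required safety evaluations as detailed in the protocol". Efficacy assessments are not mentioned.

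Other sections bear on this:

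- **The visit (Protocol 10.4).** "All study subjects will have follow-up assessments at 39 weeks after injection day in Cingal 16-02". This is the only scheduled assessment visit in 17-02. It combines the adverse event review with WOMAC, both global assessments, EuroQol and range of motion.
- **The endpoint (Protocol 12.1.1).** "The primary efficacy endpoint is the responder rate as identified by the OMERACT-OARSI responder index at 39 weeks post treatment".
- **Subjects with adverse events (Protocol 11.5.1).** "These subjects will continue to be evaluated for safety and efficacy at all scheduled follow-up points".
- **Subjects with deviations (Protocol 16.9).** "All subjects with protocol deviations will continue to be followed for safety and efficacy assessments".
- **Emergency unblinding (Protocol 14.4).** After unblinding for a serious adverse event, site staff record the subject as withdrawn.
- **Roles (Protocol 2 and 8.2).** The Treating Physician is usually the Principal Investigator, and "the treating physician is not considered blinded".
- **Missing data (Protocol 12.5, SAP 4.5).** Missing at random (MAR) is assumed. The source cited supports it where dropout is known to have nothing to do with changes in health. A missing rate below 1% is expected.

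**The concern.** Withdrawal in 17-02 stops no study treatment, because none is given. For the primary analysis, its consequence is that the week-39 responder status may never be observed. The illness example selects subjects by health state and by an expected effect on assessment. That is the kind of dropout that the plan's MAR argument sets aside. The 26-week data can inform the imputation, but an illness that starts after week 26 has left no trace in them.

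The choice may also be made by someone who knows the treatment. Section 8.2 keeps the Treating Physician out of the evaluation of effectiveness. Section 16.20 lets the Investigator, usually the same person, judge whether an illness would disturb assessment, and so influence whether an outcome is recorded. No blinded decision-maker is named. At stake is bias in the Cingal versus TH responder difference, where the TH group is small.

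**Working it through.** **1. Reading the sections together.** Section 11.1 defines an adverse event broadly enough that a new illness would normally be one. Section 11.5.1 then keeps that subject in safety and efficacy follow-up, while 16.20 allows the same subject to be withdrawn and asks only for safety data. Neither 11.5.1 nor 16.9 mentions withdrawn subjects, and 14.4 adds a second health-linked route to withdrawal. No section says which rule governs, and none asks for efficacy data after withdrawal.

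**2. The plan's own sample size.** Inputs from Protocol 12.1: difference 10 mm, SD 20 mm, two-sided 5%, 90% power, 2:1 allocation.

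n(TH) = (1 + 1/2) × (1.960 + 1.282)² × 20²/10² = 63.04, so 64 TH and 128 Cingal (t-test version 63.7). The stated 128 and 64 reproduce. At 256:64, power is 94.7%.

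**3. Is this a power problem?** The withdrawal rates below are assumptions. Their range runs from the 1% bound in 12.5 to the 15% dropout mentioned in SAP 4.1.1; Protocol 12.1 assumes none.

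| Withdrawn | TH values lost (of 64) | Cingal values lost (of 256) | Power for 10 mm, observed values only |
|---|---|---|---|
| 1% | 0.6 | 2.6 | 94.5% |
| 5% | 3.2 | 12.8 | 93.7% |
| 10% | 6.4 | 25.6 | 92.4% |
| 15% | 9.6 | 38.4 | 91.0% |

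Power for the pain difference barely moves. The documents give no power figure for the 39-week responder endpoint. The 256 and 64 are Cingal 16-02 numbers. Joining 17-02 is optional, so its actual group sizes are unknown.

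**4. Bias.** Let wC and wT be the shares withdrawn in each arm. Let g be the imputed responder rate minus the true rate among withdrawn subjects, taken as the same in both arms.

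Shift in (Cingal − TH) = (wC − wT) × g

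With g assumed between 0.2 and 0.6:

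| wC, wT | g = 0.2 | g = 0.4 | g = 0.6 |
|---|---|---|---|
| 5%, 5% | 0 | 0 | 0 |
| 5%, 10% | −1 point | −2 points | −3 points |
| 5%, 15% | −2 points | −4 points | −6 points |

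Exchanging the arms reverses the sign, so the direction is not known in advance. If fewer than 1% are missing in each arm, |wC − wT| is below 0.01 and the shift is under 1 point whatever g is.

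**5. Would the planned analyses reveal it?** Protocol 12.5 adds a per-protocol (PP) analysis and a mixed model without imputation. SAP 4.5 keeps only the PP analysis. Neither examines departures from MAR.

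**The case against.** The strongest reply is that 16.20 is silent on efficacy rather than prohibitive, and that 11.5.1 already directs efficacy follow-up for anyone with an adverse event. The illness is one item in a list of examples, not a compulsory withdrawal rule. Baseline and visits to 26 weeks remain available to the imputation, and MAR is conditional on those data. Much of this stands. It makes the matter an unresolved ambiguity whose effect depends on how sites read it.

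Several stronger readings are tempting but not supported:

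- **That 16.20 bars efficacy data, so a recalled subject would sit in clinic without completing the questionnaires.** This is inferred from silence. No section says it.
- **That 16.20 flatly contradicts 11.5.1 and 16.9.** Those sections cover subjects with adverse events or deviations and do not address withdrawal. They are in tension with 16.20.
- **That the unblinded physician often decides who is measured.** The documents say who usually holds the role, not who makes withdrawal decisions. The Blinded Evaluator collects adverse events (8.2), performs the week-39 assessments (10.4) and is counted among the Sub-Investigators (16.5). Only the illness example is tied expressly to the Investigator's judgement.
- **That withdrawal does nothing except lose the scores.** It would also bear on the medication restrictions, the washout, the diary and the rescue-use data (10.2.12, 10.2.13).
- **That a few lost TH subjects mean a bias of several points.** One TH subject is 1/64 = 1.6 points of that arm's rate and three are 4.7 points. That is the weight exposed. It becomes bias only if all three are imputed wrongly in the same direction with no offset in the Cingal arm.

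**Conclusion.** The point holds as a gap in data collection. Read as written, 16.20 can lose week-39 primary outcomes from subjects who would have provided them. The reason may be linked to health, and the decision may be made by someone who is unblinded. Loss of that kind falls outside the justification given for MAR.

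The size is unknown because the documents give no count of such withdrawals. At the missing rate that the plan expects, taken to apply in each arm, the effect on the responder difference is under 1 point. It reaches 1 to 6 points only on assumptions that the documents do not supply: withdrawal of 5 to 15%, a gap of 5 to 10 points between arms, and g of 0.2 to 0.6. With equal withdrawal and a common g it is zero. The change is worth making because it is cheap and because no later analysis can recover an outcome that was never observed.

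**What to change.** - Reword the last sentence of 16.20 so that every withdrawn subject who has not refused is asked to return for the week-39 safety and efficacy assessments: WOMAC, Patient Global Assessment, and Evaluator Global Assessment by the Blinded Evaluator.
- 16.20 already has the reason for withdrawal recorded on the eCRF. Add who made the decision, and flag the illness for the decision on the PP population.
- Reconcile 16.20 with 11.5.1, 16.9 and 14.4, so that sites know which follow-up applies when a subject has an adverse event, a deviation or an emergency unblinding and is then withdrawn.

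The list of withdrawal reasons can be left to the sponsor. Collecting the data does not require changing it.

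Cost: the visit and its forms already exist. The change needs a protocol amendment, with ethics committee approval and regulatory approval as required (16.4). Some week-39 scores will reflect the other illness. The flag identifies them for the PP decision.
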